### **Area under the Curve in the Amount of Virus RNA (RT-PCR)**

Area under the concentration–time curve (AUC) in virus RNA (RT-PCR) will be presented and is defined as AUC of change from baseline in the amount of virus RNA (RT-PCR). AUC is calculated using the trapezoidal method similar to AUC in virus titer. Patients with a positive RT-PCR result on Day 1 will be subjected to this analysis. The lower limit of quantification is defined as 2.18 for flu A and 2.93 for flu B (log10 vp/mL). If a patient is infected with multiple virus types, the sum of those the amount of virus RNA will be used for analysis.

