## **STATISTICAL ANALYSIS PLAN AMENDMENT RATIONALE**

Key changes from Version 2 to Version 3, along with the rationales for each change, are summarized below:

Section	Description of Change	Rationale for Change
Section 4.3.2	Clarified that the LLOQ will be used to impute the amount of virus RNA if less than the LLOQ. Added a table to specify the LLOQ for different assay versions.	Different assay versions have been introduced since the study start.
Section 4.4	Specify that if additional sequencing in PB1/PB2 is performed this may be reported in a CSR addendum.  Additional control virus data has been added for new lots.	Updated to clarify.  New lots have been added since study start.

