### **Change from Baseline in the Amount of Virus RNA (RT-PCR) at Each Timepoint**

Change from baseline in the amount of virus RNA (unit:  $\log_{10}$  vp/mL) will be presented and is defined as the change from baseline in the amount of virus RNA on Days 2, 4, 6, and 10.

If the amount of virus RNA is less than the lower limit of quantification, the amount of virus RNA will be imputed as the relevant LLOQ ( $\log_{10}$  vp/mL). If a patient is infected with multiple virus types, the sum of virus RNA ( $\log_{10}$  vp/mL) will be used for analysis.

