**Table 5 LLOQ for Different Assay Versions**

Influenza Type	Assay Version	LLOQ (log 10 vp/ml)
Influenza A	Version 1 50µl, 2014	2.18
	Version 1 20µl, 2019	2.48
	Version 2 20µl, 2023	2.79
Influenza B	Version 1 50µl, 2014	2.93
	Version 1 20µl, 2019	2.63

Patients with a positive by RT-PCR on Day 1 will be included in this analysis.

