#### **Area under the Curve in Virus Titer**

Area under the concentration–time curve (AUC) in virus titer will be presented and will be calculated using the trapezoidal method. AUC change from time 0 (t0) to time K (tK) is given by the formula:

$$\sum_{k=1}^K \frac{(y_k + y_{k-1})(t_k - t_{k-1})}{2}$$

where tk (hours) represents the date of the kth viral titer assessment (k=0, ..., K) and yk represents the log10 value of the kth viral titer assessment (TCID50/mL).

Twenty-four hours of time will be converted into one day. Patients with a positive virus titer on Day 1 will be included in this analysis. The lower limit of quantification and lower limit of detection is defined as 0.75 log10TCID50/mL for flu A and 0.75 log10TCID50/mL for flu B. If a patient is infected with multiple virus types, the sum of those virus titers will be used for analysis.

Additionally, the AUC in virus titer adjusted for baseline will be presented and will be calculated using the trapezoidal method. AUC of change from baseline from time 0 ( $t_0$ ) to time K ( $t_K$ ) is given by the formula

$$\sum_{k=1}^K \frac{(y_k + y_{k-1} - 2y_0)(t_k - t_{k-1})}{2}$$

where  $t_k$  (hours) represents the date of the  $k^{\text{th}}$  viral titer assessment ( $k = 0, \dots, K$ ) and  $y_k$  represents the  $\log_{10}$  value of the  $k^{\text{th}}$  viral titer assessment (TCID50/mL).

Twenty-four hours will be converted into one day. Patients with a positive virus titer on Day 1 will be subjected to this analysis. The lower limit is defined as 0.75 log10TCID50/mL for flu A and 0.75 log10TCID50/mL for flu B. If a patient is infected with multiple virus types, the sum of virus titers (TCID50/mL) will be used for analysis.

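### The virus RNA AUC paragraph keeps fixed LLOQs of 2.18 (influenza A) and 2.93 (influenza B), which conflict with the assay-version LLOQs that the SAP uses for change from baseline in RNA

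*SAP*

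**What the plan says.** All the text at issue is in the current SAP (Version 3), Section 4.3.2.

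- Under change from baseline in virus RNA, a result below the limit is handled by this rule: "the amount of virus RNA will be imputed as the relevant LLOQ". The limits follow in Table 5, titled "LLOQ for Different Assay Versions".
- The amendment rationale explains why the table was added to Section 4.3.2: "Different assay versions have been introduced since the study start".
- The RNA AUC "is defined as AUC of change from baseline in the amount of virus RNA", calculated by the trapezoidal method in the same way as the virus titer AUC.
- The RNA AUC paragraph then gives one limit per virus type: "The lower limit of quantification is defined as 2.18 for flu A and 2.93 for flu B". It mentions neither assay version nor Table 5, and it contains no imputation instruction.

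**The concern.** The AUC and the change-from-baseline table are built from the same RNA measurements, yet the section gives them different lower limits. The Version 3 revision made the limit depend on assay version, but the AUC paragraph still carries one constant per type and gives no reason for treating the AUC differently. A missed consequential edit is the likeliest explanation, though that is an inference.

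Two readings are possible. One programmer carries the values already imputed for change from baseline into the AUC. Another imputes at the constants stated in the AUC paragraph. Under the second reading one below-LLOQ sample takes two different values in two secondary endpoints, and the AUC no longer reconciles with the change-from-baseline table. With Table 5 as printed, an influenza B result below 2.63 on the 2019 assay would be set to 2.93, so it would rank above a quantified result of 2.70.

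**Working it through.** **Step 1: trace the stated constants.** Compare the AUC paragraph with Table 5 (log10 vp/mL).

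| Type | Assay version | Table 5 LLOQ | AUC paragraph | AUC paragraph minus Table 5 |
|---|---|---|---|---|
| A | Version 1, 50 µl, 2014 | 2.18 | 2.18 | 0.00 |
| A | Version 1, 20 µl, 2019 | 2.48 | 2.18 | -0.30 |
| A | Version 2, 20 µl, 2023 | 2.79 | 2.18 | -0.61 |
| B | Version 1, 50 µl, 2014 | 2.93 | 2.93 | 0.00 |
| B | Version 1, 20 µl, 2019 | 2.63 | 2.93 | +0.30 |

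The constants reproduce the 2014 rows and no others.

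**Step 2: visit weights.** The SAP formula for AUC of change (virus titer AUC paragraph, applied to RNA) is the sum over k of (y_k + y_(k-1) - 2y_0)(t_k - t_(k-1))/2. Nominal Days 1, 2, 4, 6 and 10 give t = 0, 1, 3, 5 and 9 days. The weight on each change from baseline is:

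- Day 2: (1 + 2)/2 = 1.5
- Day 4: (2 + 2)/2 = 2
- Day 6: (2 + 4)/2 = 3
- Day 10: 4/2 = 2

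The below-LLOQ weight is therefore 2 + 3 + 2 = 7 days from Day 4, 3 + 2 = 5 from Day 6, and 2 for Day 10 only.

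**Step 3: shift in the AUC.** With a quantifiable baseline, the shift is the gap times the weight (log10·days).

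| Below LLOQ | A 2023 (-0.61) | A 2019 (-0.30) | B 2019 (+0.30) |
|---|---|---|---|
| From Day 4 (×7) | -4.27 | -2.10 | +2.10 |
| From Day 6 (×5) | -3.05 | -1.50 | +1.50 |
| Day 10 only (×2) | -1.22 | -0.60 | +0.60 |

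These shifts do not depend on the baseline value.

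**Step 4: relative size.** This needs RNA profiles, which the documents do not give. Assume a baseline of 5 to 8 and a 1.5 log10 fall by Day 2, which contributes 1.5 × (-1.5) = -2.25.

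Below LLOQ from Day 4, Table 5 value against fixed value:

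- A 2023, baseline 5: -2.25 + 7(2.79 - 5) = -17.72 against -2.25 + 7(2.18 - 5) = -21.99; 4.27/17.72 = 24.1%. Baseline 8: -38.72 against -42.99, 11.0%.
- A 2019, baseline 5: -19.89 against -21.99, 10.6%. Baseline 8: -40.89 against -42.99, 5.1%.
- B 2019, baseline 5: -18.84 against -16.74, 11.1%. Baseline 8: -39.84 against -37.74, 5.3%.

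Below LLOQ from Day 6, assuming Day 4 = 3.0:

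- A 2023, baseline 5: -2.25 + 2(3.0 - 5) + 5(2.79 - 5) = -17.30 against -20.35, 17.6%. Baseline 8: -38.30 against -41.35, 8.0%.
- A 2019 and B 2019: 4-8%.

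Day 10 only, assuming Day 4 = 3.5 and Day 6 = 3.0:

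- A 2023, baseline 5: -2.25 + 2(3.5 - 5) + 3(3.0 - 5) + 2(2.79 - 5) = -15.67 against -16.89, 7.8%. Baseline 8: -36.67 against -37.89, 3.3%.
- A 2019 and B 2019: 2-4%.

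On the newer assays, imputing at the fixed limits would make the RNA decline look larger for A and, with Table 5 as printed, smaller for B. If baseline and every later visit are below LLOQ on one version, the AUC of change is 0 under either rule.

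**The case against.** The strongest reply is that the SAP largely settles the matter. The only imputation rule for RNA is the one under change from baseline, and the AUC is defined on that variable. The natural reading carries those values forward and treats the fixed limits as a leftover. That may well be what happens, but the sentence has no evident purpose in an AUC calculation other than handling results below the limit. If it has a purpose, it contradicts the other rule; if it has none, it should go.

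A second reply is that the percentages stack assumptions: the less natural reading, a newer assay, a quantifiable baseline and particular below-LLOQ days. That is fair, and they are illustrations only. The assumed Day 2 fall matters little. Protocol Section 1.2.4 reports a mean Day 2 change of -1.75 in older children; using it for A 2023 at baseline 5 gives 1.5 × (-1.75) + 7(2.79 - 5) = -18.095, and 4.27/18.095 = 23.6% instead of 24.1%.

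Third, the influenza B part is weaker. From 50 µl to 20 µl, Table 5 raises the limit by 0.30 for A but lowers it by 0.30 for B, without explanation. If the two B rows were transposed, 2.93 would match 2019 and the B example above would fall away. The A conflict would remain.

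**Conclusion.** The inconsistency is real and rests on current text. The AUC paragraph states limits that match only the 2014 assay rows as printed, for an endpoint built on a variable whose limits vary by assay version. High confidence applies to this mismatch, not to any effect on results.

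Conditional on imputing at the stated constants, the error is 0.30 to 0.61 log10 per below-LLOQ sample on a newer assay, and 0.60 to 4.27 log10·days per patient in the scenarios shown. It is zero for samples on the 2014 version, and the number of samples on each version is not given. The RNA AUC is a listed secondary virology endpoint (SAP Table 1). The SAP plans no hypothesis testing (Section 2.1), so no test, sample size or primary safety result is affected. It should be fixed because two programmers following the SAP could report different AUCs from the same data.

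**What to change.** Replace the fixed-limit sentence in the RNA AUC paragraph with: *Values below LLOQ are imputed at the Table 5 LLOQ for the assay version used for that sample, as for change from baseline.*

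Two minor clarifications can go into the same edit:

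- Confirm the two influenza B rows of Table 5, given the opposite direction of change from A.
- State the scale for summing multiple virus types. The change-from-baseline rule for RNA refers to log10 vp/mL. The first titer AUC paragraph ("the sum of those virus titers will be used for analysis") and the RNA AUC paragraph name no scale. The second titer AUC paragraph sums in TCID50/mL. Say throughout that types are summed in vp/mL or TCID50/mL before taking log10.

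The cost is one SAP sentence and short clarifications. The assay version per sample is already needed for change from baseline, so no new data are required.

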#### **4.3.2.1 Subgroup Analyses**

Subgroup analyses of the following endpoints, based on virus type and subtype, may be conducted if the numbers of patients in the relevant subgroups of the ITTi set are sufficient:

- Time to cessation of viral shedding by virus titer
- Time to cessation of viral shedding by RT-PCR

## **4.4 EXPLORATORY ANALYSES**

Exploratory efficacy analyses will be based on the ITTi set. Exploratory palatability analyses will be based patients in the ITT set who consented to Version 2 (or subsequent versions) of the Study CP40559 protocol.

### **Polymorphic and Treatment-Emergent Amino Acid Substitutions in the PA, PB1, and PB2 Genes**

Sanger sequencing of the influenza PA gene will be performed to evaluate the incidence of polymorphic (baseline vs. reference) and treatment-emergent (post-baseline vs. baseline) amino acid substitutions in treated subjects with evaluable virus. Sequencing will be performed for samples taken at baseline (Screening) and at the last evaluable timepoint (RNA titer >4 log10 vp/mL). The frequency of polymorphic substitutions will be reported in percent of total baseline samples, and the frequency of treatment-emergent

substitutions will be reported in percent of total paired samples (baseline and post-baseline sequence pair). If a RAS (resistance associated substitution) is detected, additional intermediate timepoint samples may be sequenced. Sequencing of *PB1* and *PB2* will be done for the points below according to the criteria per [Table 6](#):

- baseline viruses with reduced susceptibility to baloxavir (fold-change in  $EC_{50} > 10$  for type A viruses and  $> 5$  for type B viruses compared to reference virus in phenotypic assay). A listing of  $EC_{50}$  fold-change will be provided.
- viruses (baseline and last evaluable timepoint) without amino acid substitution in *PA*, but with reduced response to treatment or with virus rebound.

Patients meeting a criteria per [Table 6](#) will be listed and the number and proportion of patients meeting the criteria over time will be presented. PA data will be listed for all patients with an amino acid substitution. If additional sequencing in *PB1/PB2* is performed, a listing is produced for any patient with a substitution in *PB1/PB2*, which may be reported in a CSR addendum.

**Table 6 PB1 and PB2 Gene Sequencing**

Criteria	
1) Subjects who exhibit viral titer rebound:	
Viral titer at [(a certain time point) – (just before time point)] <math>\geq 2 \times SD</math> value of viral titer of control virus in assay a.
 
a Viroclinics database;
 
Influenza A - control virus data generated from 09 May 2017 until 30 November 2022 – Lot#: VC-170180018:
 
 
A/PR/8/1934: <math>3.82 + 0.36 \log_{10} \text{TCID50/mL}</math> (mean +/- SD) (<math>n = 521</math>); <math>2 \times SD = 0.72</math>
 
 
control virus data generated from 26 July 2022 until 04 May 2023 - Lot#: VC-220180034:
 
 
A/PR/8/1934: <math>2.19 + 0.49 \log_{10} \text{TCID50/mL}</math> (mean +/- SD) (<math>n = 90</math>); <math>2 \times SD = 0.98</math>
 
 
Mean SD of both lots to be used, therefore <math>2 \times SD = 2 \times ((0.36 + 0.49) / 2) = 0.85</math>
 
Influenza B - control virus data generated from 09 May 2017 until 04 May 2023:
 
 
B/Lee/1940: <math>5.33 + 0.45 \log_{10} \text{TCID50/mL}</math> (mean +/- SD) (<math>n = 516</math>); <math>2 \times SD = 0.90</math>
 

2) Subjects who continue to shed virus at Day 6 and beyond:	Viral titer ( $\log_{10}$ TCID50/mL) at Day 6 and beyond $>1.5$
3) Subjects who do not show a reduction in virus titer:	Viral titer ( $\log_{10}$ TCID50/mL) at a certain time point: A $>1.5$ Viral titer ( $\log_{10}$ TCID50/mL) at just before time point: B $>1.5$ AND Viral titer ( $\log_{10}$ TCID50/mL) at ([a certain time point: A]–[just before time point: B]) $\geq 0$

SD=standard deviation; TCID50=50% tissue culture infectious dose.

### **Drug Susceptibility in Patients with Evaluable Virus**

As assessments of the drug susceptibility of the influenza virus, the 50% effective concentration (EC50) of baloxavir will be measured by the ViroSpot™ assay using baseline swab samples. Values will be compared with values of reference strains and respective ratio (EC50 / EC50 reference) will be reported. The following influenza virus vaccine strains from 2018–2019 season will be used as reference for the ViroSpot™ assay: A/Michigan/45/2015 (H1N1)pdm09 for A/H1N1 samples, A/Singapore/INFIMH-16-0019/2016 for A/H3N2 samples from Northern hemisphere, A/Switzerland/8060/2017 for A/H3N2 samples from Southern hemisphere, and B/Colorado/06/2017-like virus (B/Victoria/2/87 lineage) and B/Phuket/3073/2013-like virus (B/Yamagata/16/88 lineage) for influenza type B samples. Mean EC50 value of the two B reference strain EC50 values will be used to calculate EC50 ratio.

### **Respiratory Coinfections (BioFire)**

Baseline samples taken as part of Study CP40559 Protocol Version 2 (or subsequent versions) will be tested for respiratory pathogens using the qualitative PCR-based FDA cleared BioFire FilmArray® Respiratory Panel 2 assay. This assay detects 17 respiratory viral or bacterial pathogens in addition to influenza A and B. Frequency and proportions for each co-infection and the proportion of patients with at least one co-infection will be presented.

### **Proportion of Patients within each Response Category for Question 1 of the Palatability Assessment**

The palatability endpoint for patients who receive the study treatment will be summarized descriptively.

The number and proportion of patients within each response category for Question 1 of the palatability assessment will be presented.

### **Proportion of Patients with Issues with the Administration of the Full Dose**

The number and proportion of patients with issues with the administration of the full dose will be presented.

## **4.5 OTHER ANALYSIS**

### **4.5.1 Summaries of Demographics and Baseline Characteristics**

Demographic and baseline characteristics (including age, sex, race/ethnicity, weight, influenza subtype, vaccination status, and age category [per ICH]) will be summarized using means, standard deviations, medians, and ranges for continuous variables and proportions for categorical variables, as appropriate. Summaries will be presented for the safety set and for the ITTi set.

Medical history data, including surgery and procedures and baseline conditions, will be summarized descriptively using the safety set. Descriptive summaries of any previous and concomitant treatment will be produced.

A listing of patients in the ITTi set who are negative by RT-PCR at baseline will be provided.

### **4.5.2 Pharmacokinetic Analyses**

The PKEP set will be used for all PK analyses. The statistical analyses of PK will be descriptive.

For patients with blood samples collected, individual plasma baloxavir marboxil, and baloxavir concentrations will be tabulated by patient and by timepoint. Individual and mean (if appropriate) plasma baloxavir marboxil and baloxavir concentrations versus time data will be plotted by age group.

As this study uses an optimized sparse PK regimen, individual PK parameters of baloxavir marboxil and baloxavir (AUC, maximum plasma concentration [ $C_{max}$ ], time to maximum concentration [ $t_{max}$ ], and terminal half-life [ $t_{1/2}$ ]) will not be determined using model-independent methods. However, individual drug concentrations determined plasma concentration 24 and 72 hours postdose ( $C_{24}$  and  $C_{72}$ , respectively) of baloxavir will be listed and summarized (mean, standard deviation, coefficient of variation, median, minimum, and maximum) by age group.

In addition, a non-linear mixed-effects model (NONMEM, Version 7.3 or higher) will be used to analyze the PK data in combination with PK data from other studies to estimate the typical population PK parameters (e.g., apparent clearance [CL/F], apparent volume of distribution for the central compartment [Vc/F]) in the pediatric population, to assess the inter-subject variability and to evaluate the impact of predefined covariates such as race and body-weight on baloxavir pharmacokinetics. Individual PK metrics, such as area under the concentration–time curve from Time 0 to infinity (AUCinf),  $C_{24}$ ,  $C_{72}$  and  $C_{max}$ , will be calculated based on individual posthoc Bayesian estimates for each patient and the impact of identified covariates will be assessed graphically and numerically. PK parameters will be tabulated and summarized (i.e., by mean, standard deviation, coefficient of variation, median, and minimum and maximum) by age group.

The population PK analysis will be described in a specific analysis plan and the population PK analysis will be reported in a dedicated modelling and simulation report.

Additional PK analyses will be conducted as appropriate.

Pediatric exposure matching to adults will use different PK metrics, such as  $C_{24}$  (observed as well as Bayesian post hoc)  $C_{72}$  and  $AUC_{inf}$  (derived as Bayesian post hoc), to assess whether exposure is sustained similarly as in adults, and to explore whether or not viral rebound, if any, may be associated with lower  $C_{72}$  values. For completeness,  $C_{max}$  will be calculated as secondary PK parameter.

Assessment of pediatric exposure and comparison to adults will use all PK data. Results may be described within the population PK report or in a dedicated extrapolation report.

#### **4.6           INTERIM ANALYSES**

An interim PK analysis is planned for this study. PK samples, up to and including those collected at Visit 4/5 of first 6 patients dosed, will be batched for an early shipment.

This will enable a timely review of the systemic plasma concentrations, in particular the  $C_{24}$  and  $C_{72}$ . This is in order to verify, in a timely manner, that exposures at the proposed doses are in reasonable agreement with the corresponding values seen in adults. The estimated turnaround time between last sample collected and data review is estimated to be approximately 2 to 3 weeks, and recruitment will continue during this time. Data review will be performed by members of the Sponsor study team.

No other interim analyses are planned for this study. However, given there is no formal statistical hypothesis testing in this study, the Sponsor may choose to conduct optional interim analyses as appropriate. The decision to conduct an optional interim analysis and the timing of the analysis will be documented in the Sponsor's trial master file prior to the conduct of the interim analysis. The interim analysis will be performed and interpreted by members of the Sponsor study team and appropriate senior management personnel.

#### **5.           SUPPORTING DOCUMENTATION**

The Study CP40559 protocol synopsis is provided in [Appendix 1](#). For additional details, see the Schedule of Assessments in [Appendix 2](#) and [Appendix 3](#).

## Appendix 1 Protocol Synopsis

**TITLE:** A MULTICENTER, SINGLE-ARM, OPEN-LABEL STUDY TO ASSESS THE SAFETY, PHARMACOKINETICS, AND EFFICACY OF BALOXA VIR MARBOXIL IN OTHERWISE HEALTHY PEDIATRIC PATIENTS FROM BIRTH TO <1 YEAR WITH INFLUENZA-LIKE SYMPTOMS

**PROTOCOL NUMBER:** CP40559

**VERSION NUMBER:** 6

**IND NUMBER:** 126653

**EUDRACT NUMBER:** 2018-002154-70

**TEST PRODUCT:** Baloxavir marboxil (RO7191686)

**PHASE:** Phase III

**INDICATION:** Influenza

**SPONSOR:** F. Hoffmann-La Roche Ltd

### **OBJECTIVES AND ENDPOINTS**

This study will evaluate the safety, pharmacokinetics, and efficacy of baloxavir marboxil in otherwise healthy patients from birth to <1 year of age with influenza-like symptoms. Specific objectives and corresponding endpoints for the study are outlined below.

Safety (Primary) Objective	Corresponding Endpoint
• To evaluate the safety of a single dose of baloxavir marboxil	• Incidence, severity, and timing of adverse events, serious adverse events, vital sign measurements, and clinical laboratory tests
Pharmacokinetic Objective	Corresponding Endpoints
• To evaluate the PK of baloxavir marboxil after single-dose administration	• Plasma concentrations of baloxavir marboxil (pro-drug) and S-033447 (active metabolite) will be summarized by time ( $C_{24}$ and $C_{72}$ ) and cohort • Population PK model derived PK parameters (e.g., $AUC_{inf}$ , $C_{max}$ , $T_{max}$ , $t_{1/2}$ (modelling report))
Efficacy (Secondary) Objectives	Key Corresponding (Secondary) Endpoint
• To evaluate the efficacy of baloxavir marboxil	• Time to alleviation of influenza signs and symptoms, defined as the length of time taken from the start of treatment to the point at which all of the following criteria are met and remaining so for at least 21.5 hours: – A score of 0 (no problem) or 1 (minor problem) for cough and nasal symptoms (items 14 and 15 of the CARIFS) – A “yes” response to the following question on the CARIFS: “Since the last assessment has the subject been able to return to day care/school, or resume his or her normal daily activity in the same way as performed prior to developing the flu?” – First return to afebrile state (tympanic temperature $\leq 37.2^{\circ}\text{C}$ )

Efficacy (Secondary) Objectives (cont.)	Corresponding Endpoint (cont.)

 
To evaluate the efficacy of baloxavir marboxil
 
	
 
Duration of fever (time to return to afebrile state [tympanic temperature <math>\leq 37.2^{\circ}\text{C}</math>] and remaining so for at least 21.5 hours)
 
Duration of symptoms (alleviation of all symptoms as defined by a score of 0 [no problem] or 1 [minor problem] and remaining so for at least 21.5 hours, for all 18 symptoms specified in the CARIFS questionnaire)
 
Time to return to normal health and activity
 
Frequency of influenza-related complications (death, hospitalization, radiologically confirmed pneumonia, bronchitis, sinusitis, otitis media, encephalitis/encephalopathy, febrile seizures, myositis)
 
Proportion of patients requiring antibiotics
 

Secondary Virology Objective	Corresponding Endpoints

 
To evaluate the virological activity of baloxavir marboxil
 
	
 
Time to cessation of viral shedding by virus titer and by RT-PCR
 
Change from baseline in influenza virus titer and in the amount of virus RNA (RT-PCR) at each time point
 
Proportion of patients with positive influenza virus titer and proportion of patients positive by RT-PCR at each time point
 
Area under the curve in virus titer and in the amount of virus RNA (RT-PCR)
 

Exploratory Efficacy Objective	Corresponding Endpoints

 
To evaluate the polymorphic and treatment-emergent amino acid substitutions and drug susceptibility in patients with evaluable virus
 
	
 
Polymorphic and treatment-emergent amino acid substitutions in the PA, PB1, and PB2 genes
 
Drug susceptibility in patients with evaluable virus
 

Exploratory Palatability Objective	Corresponding Endpoints

 
To evaluate the palatability of the oral suspension in the pediatric population
 
	
 
Proportion of patients within each response category for Question 1 of the palatability assessment
 
Proportion of patients with issues with the administration of the full dose
 

$\text{AUC}_{\text{inf}}$ =area under the concentration–time curve from Time 0 to infinity;  $\text{C}_{24}$ =plasma concentration 24 hours postdose (acceptable time window 20 to 28 hours);  $\text{C}_{72}$ =plasma concentration 72 hours postdose; CARIFS=Canadian Acute Respiratory Illness and Flu Scale;  $\text{C}_{\text{max}}$ =maximum plasma concentration; PA=polymerase acidic protein; PK=pharmacokinetic; RT-PCR=reverse transcriptase-polymerase chain reaction;  $\text{t}_{1/2}$ =half-life;  $\text{T}_{\text{max}}$ =time to maximum plasma concentration.

